9 STATISTICAL CONSIDERATIONS

9.1 General Approach

Continuous variables will be presented as means with standard deviation or median with interquartile range. All statistical tests of significance will be two-sided with alpha level 0.05. Stata will be used for all statistical analysis.

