9.2 Baseline Descriptive Statistics

Participants in the two study arms will be compared on their baseline demographics characteristics, collected from the Demographics Questionnaire, and on their operative characteristics, collected by chart review. Inferential statistics will be used to test for significant differences across study arms at baseline. To conduct these statistical tests, we will apply either standard t-tests for continuous measures or difference in proportion tests for binary measures.

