9.3 Analysis of the Primary Endpoint

The primary objective of this study is to compare drug adherence between the two study arms, and the corresponding primary endpoint of the study is the proportion of days at home during which the participant took the prescribed anticoagulant. This is defined as the proportion of days covered (PDC).

PDC = number of days of anticoagulant actually taken / number of days of anticoagulant supposed to take

Number of days of anticoagulant actually taken is determined during the POD 30 phone call by asking the participant how many pills/vials they have remaining and then subtracting that from the size of the prescription they were given. Number of days of anticoagulant supposed to take is calculated by subtracting the number of days postop the patient was discharged from 30.

PDC will be compared between the two groups using a **non-inferiority trial design** with difference in proportions test with the following hypothesis:

H₀: Apixaban is inferior to Enoxaparin in terms of the average PDC response.

HA: Apixaban is non-inferior to Enoxaparin in terms of the average PDC response.

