9.3.1 Sample Size Calculation

Prior studies suggest the at-home adherence to daily lovenox regimen is around 85%. ^{21,28,34,35} Assuming a baseline PDC in the control group of 85% and non-inferiority margin of 15%, a sample size of 45 subjects per arm, 90 subjects total, will provide 80% power to detect non-inferiority at a one-sided significance level of 0.05. ³⁶

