9.4 Analysis of Secondary Endpoints

The following secondary endpoints will be assessed to further characterize adherence and also related elements of satisfaction and cost, though analyses of these related elements are not dependent on findings of the primary endpoint.

- 1. A binary measure of adherence: adherent vs non-adherent. Adherent is defined as taking *all* intended anticoagulant. Adherence in this definition will be compared using a test of proportions (proportion of patients in one study arm that were "adherent" vs proportion of patients in the other arm that were "adherent") within the ITT and population.
- 2. Cost of the medication. There are several measures of cost that will be studied as endpoints, including overall medication cost, cost paid by insurance, and most importantly participant out of pocket cost. Cost will be measured in dollars and reported as median and as mean depending on the presence of outliers. This will be collected from pharmacy review of prescriptions. Cost will be compared using a rank sum test.
- 3. Scores on the two validated questionnaires given: PROMIS and COST. These validated questionnaires both have scoring systems and a t test of the average score of participants in each arm will be compared (ie average score on COST for participants in apixaban arm vs average score on COST for participants in enoxaparin arm). A rank sum test will be used if distributions have outliers.

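### Section 9.3 tests average PDC, a per-participant fraction, with a difference-in-proportions test and leaves unit, variance and values above 1 undefined; with participants as n and PDC within 0 to 1, power is lost

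*Combined protocol and SAP*

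**What the plan says.** Section 9.3 defines PDC as days of anticoagulant taken divided by days due, so each participant has one fractional value. The numerator comes from the POD 30 call, by "asking the participant how many pills/vials they have remaining and then subtracting that from the size of the prescription they were given". No upper limit is stated. The alternative hypothesis reads "Apixaban is non-inferior to Enoxaparin in terms of the average PDC response", and the null is also framed on the average. The arms are compared "with difference in proportions test with the following hypothesis".

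Section 9.3.1 assumes a control PDC of 85% and a 15% margin, and concludes that "45 subjects per arm, 90 subjects total, will provide 80% power to detect non-inferiority at a one-sided significance level of 0.05". It states no SD. Section 9.1 says "All statistical tests of significance will be two-sided with alpha level 0.05".

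Elsewhere the plan matches test to data type. Section 9.2, for baseline comparisons only, uses "standard t-tests for continuous measures or difference in proportion tests for binary measures". Section 9.4 makes all-or-nothing adherence a separate secondary endpoint: "Adherence in this definition will be compared using a test of proportions". For the questionnaires it plans "a t test of the average score of participants in each arm will be compared".

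**The concern.** A difference-in-proportions test takes its standard error from p(1-p)/n, which is correct for a yes/no outcome. PDC is not one: no section sets a cut-point for it, and the binary version of adherence is a different endpoint. The variance of average PDC has to come from the spread of PDC between participants.

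Three readings of 9.3 are open:

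- **(a) Participants as n**, with p the mean PDC and variance p(1-p). If PDC lies within 0 to 1, this variance is too large unless everyone scores 0 or 1. A non-inferior apixaban arm could then fail because of the formula alone.
- **(b) Days pooled as n**, treated as independent. The standard error is then too small, and non-inferiority is declared too often.
- **(c) A comparison of average PDC using the observed variance.** Neither problem arises, but the text does not say this.

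The same data can give different primary conclusions under the three readings. In an open-label trial, that choice should be fixed before analysis.

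**Working it through.** **Inputs.** From 9.3.1: 45 per arm, control mean 0.85, margin 0.15, one-sided 0.05 (z = 1.645), 80% power (z = 0.842). The SD of PDC is not in the documents, so 0.20, 0.25, 0.30 and the maximum are assumed values.

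**The plan's own figure.** The binomial formula with equal rates gives n = (1.645 + 0.842)² × (2 × 0.85 × 0.15) / 0.15² = 70.07, so 71 per arm rather than 45. At 45 per arm it gives 63.6% power. A figure of 45 appears under inputs the plan does not state: a true apixaban PDC of 0.88 (44.5, rounded up), or a comparison of means with an SD of about 0.286.

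**Variance bound.** For x between 0 and 1, x² ≤ x, so the variance is at most p - p² = p(1-p), with equality only if every value is 0 or 1. At p = 0.85 this is an SD of √0.1275 = 0.357.

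**Power under (a) against a comparison of means.** Let d be the true difference, apixaban minus enoxaparin.

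- True SE = SD × √(2/45).
- Binomial SE = 0.0753 (0.85 vs 0.85), 0.0720 (0.85 vs 0.88), 0.0866 (0.85 vs 0.70).
- Named test: Φ[(0.15 + d - 1.645 × binomial SE) / true SE].
- Means: Φ[(0.15 + d) / true SE - 1.645].

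| SD | True SE | Named, d = 0 | Means, d = 0 | Named, d = 0.03 | Means, d = 0.03 |
|---|---|---|---|---|---|
| 0.20 | 0.0422 | 0.733 | 0.972 | 0.928 | 0.996 |
| 0.25 | 0.0527 | 0.690 | 0.885 | 0.879 | 0.962 |
| 0.30 | 0.0632 | 0.661 | 0.766 | 0.835 | 0.885 |
| maximum | 0.0753 (d = 0) | 0.636 | 0.636 | 0.804 | 0.804 |

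For d = 0.03 the last row uses each arm's own maximum SD, 0.357 and 0.325. Simulation with beta-distributed PDC and a Welch test for the means (100,000 trials, SD 0.20 to 0.30) gave 0.737, 0.696 and 0.670 against 0.968, 0.878 and 0.762 for d = 0.

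**Participants scoring 0.** Section 6 has participants fill the prescription at their own cost, so some may never fill it. If a fraction f scores 0 and the overall mean stays at 0.85, the SD is at least √(0.85²/(1-f) - 0.85²): 0.283 for f = 0.10 and 0.314 for f = 0.12. Simulated power is 0.676 (named) against 0.791 (means), and 0.663 against 0.724.

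**Type I error at the margin (0.70 vs 0.85), reading (a).** 1 - Φ(1.645 × 0.0866 / true SE) = 0.0004, 0.0034, 0.0122 and 0.0292 for a common SD of 0.20, 0.25, 0.30 and 0.357. With each arm at its own maximum SD it is exactly 0.05. A common SD would have to pass √(0.3375/2) = 0.411 to exceed 0.05, which requires PDC above 1.

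**PDC above 1.** With an assumed 30-day supply, discharge on POD 7 and no units left, days due are 30 - 7 = 23 and PDC = 30/23 = 1.30. Lost or discarded units count as taken.

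**Reading (b).** Pooling k days per participant divides the binomial SE by √k. For the same four common SDs, type I error is 0.199, 0.250, 0.287 and 0.318 with k = 16 (discharge on POD 14, the last eligible day), and 0.245, 0.291, 0.323 and 0.350 with k = 24 (assumed).

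**If 9.1 governs (one-sided 0.025).** Equal-means power is 0.523, 0.519, 0.516 and 0.513 for the named test, against 0.945, 0.812, 0.660 and 0.513 for means.

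**SD that supports 80% at 45 per arm, comparing means with d = 0.** 0.15 × √22.5 / (1.645 + 0.842) = 0.286 at one-sided 0.05. With 1.960 in place of 1.645 it is 0.254.

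**One data set, three decisions.** Suppose observed means of 0.85 (enoxaparin) and 0.80 (apixaban), SD 0.25, one-sided 0.05:

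- (a) SE = √((0.1275 + 0.16)/45) = 0.0799; lower bound -0.05 - 1.645 × 0.0799 = -18.1 points, so it fails.
- (c) SE = 0.0527; lower bound -13.7 points, so it passes.
- (b) with 24 days each, SE = 0.0799/√24 = 0.0163; lower bound -7.7 points, so it passes.

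**The case against.** The best defence is that a comparison of means was intended and only the label is loose: the hypotheses speak of average PDC and 9.3.1 counts subjects. That makes pooling of days the least likely reading, so its error rates should not drive the severity. It does not settle the variance, because the named test still carries p(1-p).

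It can also be said that PDC may be meant as binary, since 9.5 plans a logistic regression on it. But 9.5 gives no cut-point, and 9.4 keeps binary adherence as a separate endpoint.

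The loss is relative to a means test and depends on an unknown SD. If apixaban is truly at 0.88, in the direction the synopsis expects, the named test stays at or above 80% in every scenario. At the maximum SD both tests give 64% with equal means, so that shortfall belongs to the sample size rather than the test. Within 0 to 1, reading (a) is conservative and does not favour a false claim. All of this stands and limits the size of the problem.

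Scoring non-fillers 0 is an assumption: taken literally, the formula could give full credit to someone who never filled the prescription and has nothing left. The handling of values above 1 and the significance level are separate questions from the choice of test, but both are needed before the analysis is fully specified.

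**Conclusion.** The concern holds. The test named for the primary endpoint does not fit the endpoint or its hypotheses, and the unit, the variance and the rule for PDC above 1 are missing. This should be fixed.

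The mismatch follows from the text alone. Its size rests on assumptions: 45 analysed per arm, PDC within 0 to 1, and an SD the plan does not give. With equal means at one-sided 0.05, the loss against a means comparison is about 24 points of power at SD 0.20, 19 at 0.25, 11 at 0.30, and none at 0.357. It is about 6 to 11 points in the zero-scorer scenarios, and smaller if apixaban adherence is truly higher.

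**What to change.** In 9.3, state that the participant is the unit of analysis and how PDC above 1 is handled. Replace the difference-in-proportions test with a confidence interval for the difference in mean PDC based on the observed between-participant variance (Welch, robust or bootstrap). Declare non-inferiority if the lower bound lies above -15 points.

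Reconcile 9.1 with 9.3.1 first, then use the matching interval: 90% if the one-sided 0.05 of 9.3.1 governs, 95% if the two-sided 0.05 of 9.1 governs.

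In 9.3.1, state the assumed SD of PDC and the resulting power at 45 per arm, and restate the 80% if the result is lower. Keep the test of proportions for the binary endpoint in 9.4.

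The cost is a wording change in 9.3, one SD and power figure in 9.3.1, and one sentence on the significance level. Data and software are unchanged. With equal means, the sample size needs revisiting only if the adopted SD exceeds about 0.286 (one-sided 0.05) or 0.254 (one-sided 0.025). Both zero-scorer scenarios exceed those limits (simulated SDs 0.288 and 0.316), so that possibility is real.

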9.3.1 Sample Size Calculation

Prior studies suggest the at-home adherence to daily lovenox regimen is around 85%. ^{21,28,34,35} Assuming a baseline PDC in the control group of 85% and non-inferiority margin of 15%, a sample size of 45 subjects per arm, 90 subjects total, will provide 80% power to detect non-inferiority at a one-sided significance level of 0.05. ³⁶

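### The 80% power in 9.3.1 does not follow from its printed inputs, and 9.1 and 9.3.1 set different alphas for the primary test

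*Combined protocol and SAP*

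**What the plan says.** Section 9.3.1 sets out the sample size in one sentence. Its inputs are "Assuming a baseline PDC in the control group of 85% and non-inferiority margin of 15" (printed as a percentage, not labelled absolute or relative), and the test is "to detect non-inferiority at a one-sided significance level of 0.05". Its conclusion is that "a sample size of 45 subjects per arm, 90 subjects total, will provide 80% power to detect non-inferiority". Section 5.3 confirms that 90 is the number to be analysed.

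Section 9.3 defines the endpoint for each participant: "PDC = number of days of anticoagulant actually taken / number of days of anticoagulant supposed to take". It compares the arms "with difference in proportions test with the following hypothesis", and the alternative hypothesis is that "Apixaban is non-inferior to Enoxaparin in terms of the average PDC response". It gives no alpha, confidence level or decision rule. Section 9.4 lists separately "A binary measure of adherence: adherent vs non-adherent", also to be compared by a test of proportions.

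Section 9.1 states: "All statistical tests of significance will be two-sided with alpha level 0.05". It makes no exception for the primary test.

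No assumed apixaban PDC and no SD of PDC appears anywhere in the document.

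**The concern.** A non-inferiority power calculation needs four things besides N: a margin, an alpha, a true difference and a variance. Section 9.3.1 prints the first two. If the variance is taken from the proportions test named in 9.3, the control value of 85% supplies it, and only the true difference is missing. If the comparison is of mean PDC, as the hypotheses in 9.3 say, the SD is missing as well. Either way a reader cannot reproduce the figure that justifies 90 participants.

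There are two further problems. The test in 9.3 is meant for yes/no outcomes, while the endpoint is a fraction for each participant. And a two-sided 0.05 test against a margin corresponds to one-sided 0.025, not the one-sided 0.05 of 9.3.1. So the power of the primary claim, and possibly its pass/fail result, depend on choices the plan leaves open.

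**Working it through.** **Inputs.** From 9.3.1: control PDC 0.85, margin 0.15, 45 per arm, one-sided alpha 0.05 (z = 1.645), 80% power (z = 0.842). From 9.1: two-sided 0.05, that is, one-sided 0.025 against a margin (z = 1.960). Assumptions, not printed: the margin is absolute, which is the natural reading for a test of a difference; the true difference and the SD are varied below. All figures use the normal approximation with unpooled variance.

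**1. The plan's figure from its own inputs.** Proportions test, 85% in both arms:
- Variance sum: 2 × 0.85 × 0.15 = 0.255.
- n per arm = (1.645 + 0.842)² × 0.255 / 0.15² = 70.07, so 71.
- SE at 45 per arm = √(0.255/45) = 0.0753.
- Power = Φ(0.15/0.0753 − 1.645) = 0.636. Exact enumeration of the Wald test gives 0.638.

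The stated 80% is not reproduced. Other methods that use only the printed inputs also fall short: restricted-likelihood (Farrington-Manning) test 63.0%, continuity-corrected test 54.5%, arcsine 53.2%.

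**2. What brings 80% back on the proportions route.** With apixaban at 0.88, the variance sum is 0.1275 + 0.1056 = 0.2331 and the distance to the margin is 0.15 + 0.03 = 0.18. Then n = (1.645 + 0.842)² × 0.2331 / 0.18² = 44.48, so 45, with power 0.804.

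**3. What brings 80% back on the mean scale, with no true difference.** Power = Φ(0.15/(SD × √(2/45)) − z). The largest SD that gives 80% is 0.15 × √(45/2)/(1.645 + 0.842) = 0.286 (0.284 with a t distribution).

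**4. Power at 45 per arm under each alpha.**

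| Scenario | One-sided 0.05 | One-sided 0.025 |
|---|---|---|
| Proportions, 85% vs 85% | 64% | 51% |
| Proportions, apixaban 88% | 80% | 71% |
| Means, no difference, SD 0.20 | 97% | 94% |
| Means, no difference, SD 0.25 | 89% | 81% |
| Means, no difference, SD 0.286 | 80% | 70% |
| Means, no difference, SD 0.30 | 77% | 66% |

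**5. The test against the endpoint.** For a variable between 0 and 1 with mean 0.85, the SD cannot exceed √(0.85 × 0.15) = 0.357. That maximum is reached only if every participant scores 0 or 1, and it is the variance the proportions test uses. Applied to average PDC with one value per participant, the test therefore generally overstates the standard error.

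**6. What the alpha can change.** At SD 0.286 (the value that gives 80%, used only as an illustration), SE = 0.0603. Non-inferiority needs an observed difference above −0.15 + 1.645 × 0.0603 = −0.051 with a 90% interval, or above −0.15 + 1.96 × 0.0603 = −0.032 with a 95% interval. A result between −5.1 and −3.2 points passes under one and fails under the other.

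**The case against.** The strongest reply is that a zero true difference is not the trial's expectation. The synopsis (1.1) hypothesises greater adherence on apixaban. Section 2.2 describes a retrospective comparison with compliance events of 0% on apixaban and 33.5% on enoxaparin. Section 4 plans a superiority test if non-inferiority is met. An apixaban PDC of 88% gives exactly 45 per arm, which fits an unprinted assumption better than a miscalculation. This stands as far as it goes: the documents do hint at an advantage. But the synopsis also hypothesises non-inferior adherence, the retrospective source was not randomised and did not report PDC, and no passage gives a PDC value for apixaban. A match at 88% does not show where the 45 came from.

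A second reply is that PDC is nearly continuous, so the binomial variance is pessimistic. That is correct, and it is why 64% should not be taken as the trial's real power. It also means that 9.3 names a test that does not fit its hypotheses and that 9.3.1 omits the SD.

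On alpha, 9.1 is headed as a general approach and 9.3.1 can be read as the specific rule for non-inferiority. That reading is reasonable, but 9.3.1 describes the sample size, and 9.3, which governs the analysis, does not settle the matter.

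A reader might infer that the trial is underpowered, that the sponsor made an arithmetic error, or that 64% is a floor. The documents support none of these. Step 4 shows power well above 80% at moderate SDs, and an unprinted input can explain the 45. The 64% belongs to exactly zero difference: with apixaban at 83%, power is Φ(0.13/√((0.1275 + 0.1411)/45) − 1.645) = 0.515.

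**Conclusion.** The point holds as an unsupported power statement. On the printed inputs, read with an absolute margin, the test in 9.3 and no true difference, 45 per arm gives about 64%, some 16 points below the stated figure. Reaching 80% requires an apixaban advantage of about 3 points or an SD of PDC no larger than about 0.286, and the plan prints neither. Values on both sides of 80% are possible, and the documents do not let a reader choose between them.

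The difference in alpha between 9.1 and 9.3.1 is real and is not resolved in 9.3. Its size is about 10 points of power in either scenario that reaches 80%. The mismatch between a proportions test and a hypothesis about average PDC is a separate defect in 9.3, and it generally makes the standard error too large. These items affect the primary conclusion and should be corrected.

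**What to change.** 1. **Section 9.3, test.** Compare mean PDC between arms with an unequal-variance confidence interval for the difference. Keep the test of proportions for the binary measure in 9.4.
2. **Section 9.3.1, power.** State that the margin is 15 percentage points absolute. Restate the power with the SD (or apixaban PDC) it rests on and the source of that value, and show power at zero difference over a range of SDs, as in the table above. If the proportions test is kept with no assumed difference, state about 64%. An apixaban PDC above 85% should come from a cited source and not be chosen to reach 80%.
3. **Sections 9.1 and 9.3, alpha and rule.** Either exempt the primary non-inferiority test from the two-sided default in 9.1, or restate the power at one-sided 0.025. Add to 9.3 that non-inferiority is declared if the lower limit of the two-sided interval for apixaban minus enoxaparin mean PDC exceeds −15 points. Use one level only: 90% for one-sided 0.05 or 95% for one-sided 0.025.

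The changes are wording in three sections, with no extra patients if the power is restated. The cost is a power statement that is less favourable or openly conditional, and choosing the 95% interval lowers either 80% scenario to about 70%. For comparison, holding 80% with the proportions test, one-sided 0.05 and no true difference would need 2 × 71 = 142 analysed participants instead of 90.

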9.4 Analysis of Secondary Endpoints

The following secondary endpoints will be assessed to further characterize adherence and also related elements of satisfaction and cost, though analyses of these related elements are not dependent on findings of the primary endpoint.

- 1. A binary measure of adherence: adherent vs non-adherent. Adherent is defined as taking *all* intended anticoagulant. Adherence in this definition will be compared using a test of proportions (proportion of patients in one study arm that were "adherent" vs proportion of patients in the other arm that were "adherent") within the ITT and population.
- 2. Cost of the medication. There are several measures of cost that will be studied as endpoints, including overall medication cost, cost paid by insurance, and most importantly participant out of pocket cost. Cost will be measured in dollars and reported as median and as mean depending on the presence of outliers. This will be collected from pharmacy review of prescriptions. Cost will be compared using a rank sum test.
- 3. Scores on the two validated questionnaires given: PROMIS and COST. These validated questionnaires both have scoring systems and a t test of the average score of participants in each arm will be compared (ie average score on COST for participants in apixaban arm vs average score on COST for participants in enoxaparin arm). A rank sum test will be used if distributions have outliers.

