4 STUDY DESIGN

This is a pragmatic, multi-site, randomized, controlled trial comparing two anticoagulant medications, enoxaparin and apixaban, when given to bladder cancer patients as VTE prophylaxis after RC.

The primary objective of the study is to assess participant adherence to the at-home anticoagulation regimen. Other objectives include participant satisfaction and cost burden. At 30 days postop study team members will call participants to assess the primary endpoint of adherence as well as secondary endpoints of cost and patient satisfaction. At 90 days the participants will receive another phone call to complete one additional questionnaire assessing financial burden since surgery. While both drugs are considered standard of care for EP after RC, apixaban is considered the intervention arm due to its more recent introduction and use at this institution. The study is powered to detect if adherence to apixaban is noninferior to enoxaparin. If this criterion is met the study will also test for the superiority of apixaban.

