7 STUDY ASSESSMENTS

At the time of enrollment, participants will be offered to complete the Demographics questionnaire either in person (if applicable), via phone (if applicable), or via a secure REDCap link emailed to them.

Participants will be contacted via phone on POD30 and POD90. During the phone call, participants will be given the option to receive an email with a secure link to REDCap to complete the majority of the study visit electronically (PMAS, Patient Satisfaction, and COST

questionnaires). Medication counting and screening for adverse events including VTE and bleeding must be done over the phone rather than via emailed link.

Study assessments will be conducted by staff other than the treating physician, and staff members will clearly state the contact is part of the research study, not part of routine clinical care.

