9.5 Exploratory Analysis

Analysis of other factors influencing adherence to at home anticoagulation in this population are considered exploratory. To explore what factors other than type of anticoagulant may be impacting adherence, we plan to perform a logistic regression with the outcome variable of PDC. Covariates will include the following: age, gender, ethnicity, marital status, living situation, occupational status, education level, annual household income, insurance status, history of prior blood clot, number of daily medications, discharge destination, study arm, and items from the Satisfaction Questionnaire. Univariate regression will be performed first followed by multivariate regression including all variables that were significantly associated on univariate regression.

A second exploratory analysis will be comparing elements of the novel satisfaction questionnaire trial between the apixaban and enoxaparin arms. Items from this questionnaire may be compared by presenting descriptive statistics without formal tests for statistical significance in order to explore how patient satisfaction varies between the study arms and allow future physicians to give anticipatory guidance.

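### The POD90 COST comparison is valid but less precise than it could be: it uses no baseline score and none of the income, insurance and site data that the trial holds.

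*Combined protocol and SAP*

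**What the plan says.** COST is scheduled once. Section 4 states: "At 90 days the participants will receive another phone call to complete one additional questionnaire assessing financial burden since surgery". The schema in section 1.2 also shows it only at the POD90 call. Before surgery the only instrument is the demographics form (section 7: "At the time of enrollment, participants will be offered to complete the Demographics questionnaire"), so there is no baseline COST score.

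For the analysis, section 9.4 says that "a t test of the average score of participants in each arm will be compared", spelled out for COST as "average score on COST for participants in apixaban arm vs average score on COST for participants in enoxaparin arm", with the fallback "A rank sum test will be used if distributions have outliers". Neither test takes covariates.

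Section 9.5 lists "annual household income, insurance status, history of prior blood clot" among its covariates, but the outcome of that model is PDC. No section specifies a covariate model for COST. Section 4.1 describes two sites and simple 1:1 allocation, with no stratification stated. Section 9.1 sets two-sided alpha at 0.05. Section 9.7 treats missing data as random and drops them from every analysis.

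**The concern.** According to section 7.2, COST captures distress over healthcare costs in general, not the price of the anticoagulant alone. A patient's financial position before surgery can therefore be expected to contribute to the score at day 90. In an unadjusted comparison that contribution stays in the error term.

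The plan already intends to record variables that could remove part of it. Section 7.3 says the demographics form is there to show which sociodemographic factors may influence the endpoints, yet section 9 follows this through only for adherence. What is at stake is the width of the confidence interval for a secondary endpoint. The validity of the comparison is not in question.

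**Working it through.** **Inputs from the documents.** The analysed sample is 45 per arm, 90 in total (section 9.3.1), from 108 enrolled (section 5.3). Alpha is two-sided 0.05 (section 9.1).

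**The plan's own figure.** No sample size, SD, expected difference or power is given for COST. The 45 per arm comes from the primary PDC calculation. With the inputs stated there (85% in both arms, margin 15%, one-sided 0.05, 80% power), the formula for two proportions gives (1.645 + 0.842)² × 2 × 0.85 × 0.15 / 0.15² = 70.07 per arm, so 45 is not reproduced. That concerns the primary endpoint. Here 45 is used only as the number of participants the plan expects to analyse.

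**Assumed inputs.** R² is the share of COST variance explained by pre-randomisation covariates. The documents give no value. I take 0.10-0.25 for income, insurance and site, and 0.36-0.50 with a baseline COST score.

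**Detectable difference at 80% power, in SD units:** (1.960 + 0.842) × √(2/n) × √(1 − R²).

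- Unadjusted, n = 45: 2.802 × √(2/45) = 2.802 × 0.2108 = 0.59. If all 108 responded (n = 54) it would be 0.54.
- Power for a true difference d: Φ(d × √(n/2) / √(1 − R²) − 1.960).
- Equivalent unadjusted sample size: 90 / (1 − R²).

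| R² | Detectable difference (SD) | Power for 0.3 SD | Power for 0.5 SD | Equivalent total N |
|---|---|---|---|---|
| 0 (as planned) | 0.59 | 30% | 66% | 90 |
| 0.10 | 0.56 | 32% | 71% | 100 |
| 0.25 | 0.51 | 38% | 78% | 120 |
| 0.36 | 0.47 | 43% | 84% | 141 |
| 0.50 | 0.42 | 52% | 92% | 180 |

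The noncentral t distribution gives nearly the same answers: 29% for 0.3 SD unadjusted, and 51% at R² = 0.50 with three covariate parameters.

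**Loss for degrees of freedom.** With k covariate parameters the variance rises by about (90 − 3)/(90 − k − 3).

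- k = 3: 87/84 = 1.04. k = 5: 87/82 = 1.06. k = 8: 87/79 = 1.10.
- At k = 5 the net variance factors are 0.90 × 1.06 = 0.95 and 0.75 × 1.06 = 0.80. The detectable differences become about 0.58 and 0.53 SD.
- At k = 8 and R² = 0.10 the factor is 0.90 × 1.10 = 0.99, so almost nothing is gained.

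**Loss from missing covariates.** If 10% did not report income (assumption) and were dropped under section 9.7, 81 of 90 would remain. At R² = 0.10 the variance factor is then 0.90 × 90/81 = 1.00, and the gain is gone.

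**The case against.** The strongest reply is that the planned test contains no error. Randomisation makes the unadjusted comparison valid, and the plan never claims that COST is powered. Section 9.4 names out-of-pocket cost as the most important cost measure, so COST supplements it. Adjustment uses degrees of freedom and, under the section 9.7 rule, could lose participants: the demographics form is only offered, and income may go unreported. Every figure for the gain rests on an assumed R².

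All of this stands, and it limits the point to a modest improvement. It also shapes the remedy: few and coarse categories, and a rule for unreported values.

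A reader might go further and infer that a chance imbalance in income could pass for a drug effect. The documents do not support that as a defect. Such imbalances are already reflected in the standard error and the 5% error rate of the t test, and section 9.2 would display an imbalance in recorded characteristics.

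A reader might also infer that the drug's effect on COST must be small beside differences between people. The documents give no COST variability. Table 1 in section 2.3 supports a modest copay contrast only indirectly: copays of $20 or less for 211 of 269 (78%) on enoxaparin and 29 of 47 (62%) on apixaban, from binned, single-institution, non-randomised data.

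**Conclusion.** The point holds as a matter of precision on a secondary endpoint, and its priority is low. The planned test detects about 0.59 SD with 80% power. Using data the trial already intends to hold might bring this to about 0.56-0.51 SD before the loss for degrees of freedom. A baseline score might bring it to about 0.47-0.42 SD, so the larger part of the gain would come from measuring COST at enrolment. These ranges depend wholly on the assumed R² values and on 45 analysed per arm.

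Two stronger conclusions should not be drawn. A null result from the planned test would not be worthless; it would have a wide interval. Nor would adjustment make COST well powered: for a true difference of 0.3 SD, power is about 52% even at R² = 0.50.

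**What to change.** In section 9.4, make the COST comparison a prespecified linear model of the POD90 score on arm, site, household income in a few coarse categories, and insurance status. Give income and insurance a 'not reported' category, so that no participant with a POD90 score is dropped under the section 9.7 rule. Report the adjusted difference with its 95% confidence interval, and keep the planned t test or rank sum test as a sensitivity analysis.

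Preferably, add the 12 COST items to the enrolment REDCap questionnaire and include that score as a covariate. Enrolment precedes surgery and randomisation, so the score cannot be affected by the assigned drug. If recruitment has begun, the score will exist only for those still to enrol, and the model needs a stated way of handling its absence in the others.

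The adjustment costs a change of wording and a few degrees of freedom. The baseline score costs 12 more questions on an existing form and no extra visit.
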